#### **11.1 Primary endpoint analysis**

#### **Exploristics Limited**

### Identifier: EXP20012 Clinical Study Identifier: 132333

The primary endpoint will be compared between groups using a repeated measures mixed model, adjusted for age, gender, BMI, baseline CRP value (defined as the last CRP measurement prior to randomisation, or the first CRP following Dexamethasone for HCs), time from baseline, and whether they have a key comorbidity, defined as one or more of hypertension, diabetes or cardiovascular disease. An interaction between treatment and time from baseline will also be included in the model. CRP measurements more than 7 days after randomisation (or date of first CRP measurement following Dexamethasone initiation for HCs) will be removed from the analysis, so the comparison is over 7 days.

Due to the treatment by time interaction effect being included in the model, examining the treatment effect alone would be an inappropriate comparison, therefore the least squares means and 95% confidence intervals at the mean follow-up time will be compared between arms, which will take into account both the treatment effect and the treatment by time interaction. These means will be presented on the real scale, e.g. taking the antilog of the least squares mean if the dependent variable has been log-transformed. The difference between the least squares means (on the scale the model was fitted) and the standard error of the difference will be used to generate a treatment z-score, which will be compared against the normal distribution with mean 0 and variance 1, to obtain the two-sided p-value.

In addition, a supplementary analysis will be conducted where the area under the log(CRP) curve will be calculated for each individual up to 7 days of follow-up, divided by the number of days that the individual has been followed up for, to get a standardised area under the curve. The area will be calculated by assuming a linear line between the log(CRP) measurements, regardless of the time between measurements. If measurements are available after day 7, they will be excluded, and the last available log(CRP) measurement prior to day 7 will be used to calculate the area; for example, if the last measurement within 7 days of randomisation for a given individual was on day 4, but they have a day 10 measurement available, the area up to day 4 will be calculated, and divided by 4 to get the standardised area. A linear model will then be fitted, with standardised area under the log(CRP) curve as the outcome, adjusted for age, gender, BMI, log(baseline CRP value) (defined as the last log(CRP) measurement prior to randomisation, or the first log(CRP) following Dexamethasone for HCs) and whether they have a key comorbidity, defined as one or more of hypertension, diabetes or cardiovascular disease. A two-sided p-value will be calculated by comparing the z-score from the Wald test of the treatment effect against the normal distribution with mean 0 and variance 1.

Finally, as a supplementary analysis, the primary analysis will be performed, but including the HCs from the second propensity score matching analysis, where the matching was performed using the last pre-Dexamethasone CRP as opposed to the baseline CRP as defined above. The same model will be fitted for this analysis as the primary analysis, but the model will be adjusted for their last pre-Dexamethasone CRP as opposed to baseline CRP.

Prior to analysis, the primary endpoint will be assessed for conformance to normality assumptions and the appropriate transformation will be conducted if necessary. This model-based approach is likely to be more robust to missing or spurious data. Treatment effect will be declared significant at the 5% level of significance.

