#### 8.2 Independent Variables

For the primary endpoint analysis, the independent variables included in the model will be treatment (dornase alfa vs. no dornase alfa), age, gender, BMI, baseline CRP level (defined as the last CRP value prior to randomisation, or the first CRP following Dexamethasone for HCs), time from baseline and whether they have a key comorbidity, defined as one or more of hypertension, diabetes or cardiovascular disease. An interaction term between treatment and time from baseline will also be included in the model.

For secondary endpoint analyses, the same covariates will be included in the models as for the primary endpoint analysis.

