#### 8.3 Examination of Subgroups

#### 8.3.1 Primary endpoint analyses

At the interim and final analyses, the primary analysis will be to combine the two sets of individuals on BAC only in the comparator population to the individuals randomised to BAC + dornase alfa.

However, three additional analyses will be carried out at the final analysis for the primary endpoint analysis.

- 1. A comparison of the BAC + dornase alfa arm to those randomised to BAC only (no historical controls)
- 2. A comparison of the BAC + dornase alfa arm to matched historical controls (no individuals randomised to BAC only)
- 3. A comparison of those randomised to BAC only to matched historical controls (within control comparison).

The treatment effect estimate will be compared between the primary analysis and analyses 1. and 2. above. No formal test will be carried out to test the difference in treatment effect between the three analyses, but substantial differences will be noted.

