### **Exploristics Limited**

### Identifier: EXP20012 Clinical Study Identifier: 132333

In analysis 3., no treatment effect will be included in the model, since all individuals are on BAC only. Instead, a covariate will be included to indicate whether the individual is a historical control or a randomised individual.

In addition, analyses stratified by BAC treatment will be carried out for the primary endpoint.

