### **10.2 Demographic and Baseline Characteristics**

Baseline characteristics will be summarised by treatment (BAC + dornase alfa vs. BAC only) and by population: BAC + dornase alfa, randomised to BAC only, matched historical controls.

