#### **Exploristics Limited**

### Identifier: EXP20012 Clinical Study Identifier: 132333

The following baseline characteristics will be presented:

- Age
- Gender
- Ethnicity
- BMI
- Baseline CRP (defined as the last CRP value prior to randomisation, or the first CRP following Dexamethasone for HCs)
- Whether they have a key comorbidity, defined as one or more of hypertension, diabetes or cardiovascular disease
- White blood cell count
- Neutrophil count
- Lymphocyte count
- Monocyte count
- Eosinophil count
- Basophil count
- Procalcitonin
- D-dimer count
- Ordinal score (WHO scoring tool), using randomized individuals only.
- Last Pre-Dexamethasone CRP (mg/L)
- Days between diagnosis and hospitalization
- Days between hospitalization and baseline
- Days between Dexamethasone initiation and baseline

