#### 11. ANALYSIS CORRESPONDING TO THE STUDY OBJECTIVES

To identify individuals to include in the analysis from the historical controls cohort, the matching procedure will include an initial application of the study inclusion and exclusion criteria to identify the subjects that meet the criteria within the database. Further matching will involve the use of propensity scores to select the controls that most closely match with participants in the active treatment group. The propensity score model will be a logistic regression including all individuals randomised to dornase-alfa and all HCs, with an indicator variable as the outcome to indicate whether the individual is randomised or in the historical control cohort, and covariates included in the model for age, gender, BMI, baseline CRP (defined as the last CRP value prior to randomisation, or the first CRP following Dexamethasone for HCs), and whether they have a key comorbidity, defined as one or more of hypertension, diabetes or cardiovascular disease. The propensity matching will be done using a nearest neighbour approach.

Two controls will be matched for each participant in the active group.

As a supplementary analysis, the propensity score matching will be repeated, but instead of matching on baseline CRP as defined as the last CRP value prior to randomisation, or the first CRP following Dexamethasone for HCs, the matching will be done using the last pre-Dexamethasone CRP measurement, as well as the other factors defined above.

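### The primary CRP analysis starts trial patients at randomisation but historical controls at their first CRP after dexamethasone, and the dexamethasone-to-baseline interval is tabulated but not adjusted for

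*SAP*

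**What the plan says.** - SAP 8.2 adjusts for "baseline CRP level (defined as the last CRP value prior to randomisation, or the first CRP following Dexamethasone for HCs"), and SAP 11 matches on the same split definition: "baseline CRP (defined as the last CRP value prior to randomisation, or the first CRP following Dexamethasone for HCs").
- SAP 11.1 removes from the analysis "CRP measurements more than 7 days after randomisation (or date of first CRP measurement following Dexamethasone initiation for HCs"). The 7-day window therefore starts at randomisation for trial patients. For historical controls it starts on the date of the first CRP after dexamethasone.
- SAP 10.2 lists "Days between Dexamethasone initiation and baseline" among the baseline characteristics, shown "by population: BAC + dornase alfa, randomised to BAC only, matched historical controls". The interval appears nowhere else.
- SAP 8.3.1 pools randomised BAC patients and matched historical controls as the comparator at both interim and final analysis. It adds, at the final analysis, "A comparison of the BAC + dornase alfa arm to those randomised to BAC only (no historical controls") and "A comparison of those randomised to BAC only to matched historical controls (within control comparison"). It also says: "In addition, analyses stratified by BAC treatment will be carried out for the primary endpoint".
- SAP 11 and 11.1 add a supplementary re-match and re-fit using the last CRP before dexamethasone.
- SAP 6.2 removes patients who began dornase alfa before dexamethasone from the per protocol set only.

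**The concern.** CRP is drawn daily or on alternate days (SAP 3), so a control's baseline falls within a day or two of dexamethasone start by construction. A trial patient's baseline has no such anchor. Eligibility does not mention dexamethasone, background care follows hospital guidelines (Protocol 6.5), and randomisation may be up to 3 days after admission.

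Matching and adjusting on baseline CRP equates the level, not the position on the falling curve. A patient at 80 mg/L shortly after dexamethasone and one at 80 mg/L three days later may have different falls ahead. The model's time term cannot repair this, because it runs from each group's own zero. Any difference enters the pooled estimate, its 5% test and the interim conditional power. The same baseline definitions carry into the area-under-the-curve analysis and the secondary laboratory models.

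**Working it through.** **1. The plan's own figure.** Inputs (SAP 5): control mean 99 mg/L, SD 62, 40% reduction, 80% power, 5%, ratio 1:2. Difference = 0.40 × 99 = 39.6 mg/L. A two-sided two-sample t-test with 30 v 60 has 80.7% power, and 90 is the smallest 1:2 total that reaches 80%. The figure reproduces. It gives the yardstick: a CRP ratio of 0.6.

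**2. Exposure.** SAP 12 plans 30 dornase alfa, 10 randomised BAC and 60 historical controls. Share of comparators with the other starting point = 60/70 = 86%.

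**3. Where the interval is used.**

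| Place | Terms | Interval included? |
|---|---|---|
| Propensity score (SAP 3, 11) | age, gender, BMI, baseline CRP, key comorbidity | no |
| Primary model (SAP 8.2, 11.1) | the same, plus treatment, time from baseline, treatment × time | no |
| Baseline table (SAP 10.2) | descriptive, by group | yes |

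**4. Illustration. All curve and timing inputs are assumptions.** Log-scale SD = √ln(1 + (62/99)²) = 0.575. Log CRP falls by f(t) = A(1 − 2^(−t/1.5)), t days after dexamethasone, with A = 0.7 or 1.4. Let d be days from dexamethasone to baseline, u the patient's level (normal, SD 0.575) and s the slope of follow-up on u.

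- Baseline = u − f(d). Follow-up = s·u − mean of f(d + k), with k = 2, 4, 6 (Days 3, 5, 7).
- For this curve, follow-up − s × baseline = constant + (s − m)·f(d), where m = mean of 2^(−k/1.5) = (0.397 + 0.157 + 0.063)/3 = 0.206. The bias is therefore driven by (s − m) times the group difference in f(d). It vanishes near s = 0.2. If log CRP falls at a constant rate, m = 1 and it vanishes at s = 1.

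Regression on treatment and baseline, large sample, 30/10/60 mix, no drug effect. Control baselines are uniform over 0-1 or 0-2 days. The four values in each cell are A 0.7 with 0-1 and 0-2, then A 1.4 with 0-1 and 0-2:

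| Trial baselines | s = 1 | s = 0.5 | s = 0.2 |
|---|---|---|---|
| (i) uniform 0-3 days | +12.5, +5.2, +23.2, +9.1% | +4.5, +1.9, +8.1, +3.3% | within 0.2% |
| (ii) uniform 0-0.5 day | −4.2, −10.5, −8.0, −18.1% | −1.6, −4.0, −3.0, −7.1% | within 0.1% |

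A plus sign works against dornase alfa. A true 40% reduction reads as 1 − 0.6 × (1 + bias):
- s = 0.5: 35-39% in (i), 41-44% in (ii).
- s = 1: 26-37% in (i), 42-51% in (ii).

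With d as a covariate at s = 1, the bias is within 2% in (i) and about 1% in (ii). Dornase alfa v randomised BAC alone shows none (within 0.1%).

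**5. What the planned checks can see.** If follow-up SD stays at 0.575, the residual SD after baseline adjustment is 0.575·√(1 − s²).

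- *Dornase alfa v randomised BAC (30 v 10), 40% reduction.* Raw scale, unadjusted: 40% power. Log scale, unadjusted: SE = 0.575·√(1/30 + 1/10) = 0.210, z = 0.511/0.210 = 2.43, power 68%. At s = 0.2: SE 0.206, about 70%. At s = 0.5: SE = 0.498 × 0.365 = 0.182, z = 2.81, about 80%. Near 100% at s = 1.
- *Randomised BAC v historical controls (10 v 60), power for the artefact.* About 5-36% at s = 0.5 to 0.8. At s = 1 in the illustration it is 39-100% in (i) and 74-99% in (ii).
- *Baseline table, scenario (i).* (1.5 − 0.5)/√(0.75/40 + 0.083/60) = 7.0, or (1.5 − 1.0)/√(0.75/40 + 0.333/60) = 3.2 standard errors. It would reveal the misalignment but not correct the estimate.

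**The case against.** The strongest reply is that the sizes are assumed and the plan already holds safeguards. Much of this stands.

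- *Large bias together with weak checks.* A reader might infer that the bias could reach 23% and that every check is too weak to show it. The two do not hold together. The bias is that large only where follow-up tracks baseline almost perfectly, and there the baseline-adjusted checks are precise. What remains is the middle range, where the bias is a few to perhaps ten-odd percent and the within-control comparison would usually miss it.
- *Known direction.* A reader might infer that controls, indexed earlier on a falling curve, make dornase alfa look better. That ignores the adjustment for baseline CRP; with it, scenario (i) runs the other way. Scenario (i) also borrows the 3-day admission window and assumes the CRP is drawn at randomisation. If the draw is 0-1 or 0-2 days earlier (floored at dexamethasone start, follow-up counted from the draw), the slope-1 bias becomes −0.5% to +12%, or −8% to +3%.
- *Unhandled patients.* A reader might infer that trial patients without prior dexamethasone have no stated place in the analysis. SAP 6.1, 6.2 and 8.2 largely settle this: they stay in the primary set with their last CRP before randomisation as baseline. Only the pre-dexamethasone supplementary analysis, and the coding of the interval once it is used, are open.
- *Existing comparison.* SAP 8.3.1 already sets the randomised-only estimate beside the pooled one and notes substantial differences. That is a real safeguard.

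The other planned analyses do not answer the point. The re-match changes the CRP value used, not day 0. The BAC strata and the per protocol repeat do not align the day either.

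**Conclusion.** The mismatch is in the text, affects 86% of the comparators, and is corrected by none of the planned analyses that include historical controls. It can bias the pooled CRP estimate, but the documents give neither the intervals nor the shape of the fall, so neither size nor direction can be stated. About 2-8% either way is a moderate illustration (slope 0.5). The +5% to +23% and −4% to −18% ranges are extremes. The bias is about zero at slope 0.2, or at slope 1 with a constant rate of fall. The documents do not support saying that the result is biased in favour of dornase alfa, or that the randomised-only check is inadequate: its power runs from about 40% unadjusted on the raw scale to about 80% or more with baseline adjustment at slope 0.5 or above. This is a cheap improvement worth making, not a defect that invalidates the trial.

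**What to change.** 1. Add days from dexamethasone start to baseline to the propensity score and the primary model, and show its overlap by group.
2. Where overlap is thin, instead index each historical control at the CRP on the same day since dexamethasone as its matched trial patient, and apply eligibility on that day. In scenario (i), one third to two thirds of trial patients lie beyond every control's interval, so a covariate alone would extrapolate.
3. Keep the trial 7-day window starting at randomisation. State that follow-up time counts from randomisation in trial patients and from the aligned index date in controls. Starting the window at the CRP draw would be harmful: Protocol 8.1 allows screening up to 3 days before treatment, and a draw 2 days before Day 1 puts Day 7 at 6 + 2 = 8 days, outside the window.
4. State how the interval is coded for trial patients with no dexamethasone, or with a baseline before it.
5. Interpret the pooled result beside the randomised-only estimate that is already planned.

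Cost: SAP wording and re-programming; the interval is already derived for the baseline table. The propensity score goes from five to six covariates for 30 treated patients. The standard error rises by about 3-16% in the illustrations, and close matches may be fewer. The illustrations tested the covariate in a large sample without matching, so its behaviour at the planned size should be checked.

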#### 5. SAMPLE SIZE CONSIDERATIONS

Sample size calculations were produced using the proc power function in SAS Version 9.4. These were conducted to achieve 80% power to detect a difference in the active arm versus the control group at the 5% level of significance. Based on a mean of 99mg/L in the control group and a common standard deviation of 62mg/L derived from the literature [2, 3], a total sample size of 90 participants would provide sufficient power to detect a greater than a 40% relative difference for CRP in the dornase alfa group compared to the control group. Given the reported average values in severe and non-severe participants and on clinical observations from COVID-19 patients, this difference would be achievable and clinically relevant.

This study will use existing data collected at UCLH from participants admitted with COVID-19 as a comparator group. Participants in the database will be selected to act as controls as follows:

- Apply the inclusion and exclusion criteria of the COVASE study where the appropriate data are available
- Additional selection to identify closest matches

This will give the correct ratio of active versus comparator (ratio of 1:2). To achieve the required power, this would result in 30 participants in the active treatment group and at least 60 in the control. An additional 10 participants will be recruited as a control for the exploratory objectives

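### SAP 11.1 refers the primary CRP contrast and the AUC regression to the standard normal, so the nominal 5% tests are slightly too liberal; the fix is a t reference

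*SAP*

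**What the plan says.** SAP 11.1 fits a repeated measures mixed model to CRP over 7 days. It compares the arms through least-squares means at the mean follow-up time. The difference and its standard error give a z-score, "which will be compared against the normal distribution with mean 0 and variance 1, to obtain the two-sided p-value".

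The supplementary analysis in the same section fits a linear model to each patient's standardised area under the log(CRP) curve. Its two-sided p-value comes from "comparing the z-score from the Wald test of the treatment effect against the normal distribution with mean 0 and variance 1". The section ends: "Treatment effect will be declared significant at the 5% level of significance".

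SAP 8.3.1 adds further analyses of the primary endpoint. One compares dornase alfa with the patients randomised to best available care alone, leaving out the historical controls. It gives no reference distribution of its own. SAP 11.2 reuses the primary model for several secondary endpoints, including the WHO ordinal score in randomised patients only.

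Neither document names a t distribution, a degrees-of-freedom method, or REML or ML as the estimator for these models. Protocol 11.3.2 gives no reference distribution. SAP 11.1 asks for 95% confidence intervals for the least-squares means without saying how they are formed.

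**The concern.** An estimate divided by an estimated standard error has heavier tails than the standard normal. Comparing it with 1.96 therefore rejects a true null hypothesis more often than 5% of the time, and the excess grows as the number of patients falls. In this trial the primary analysis has about 100 patients. The only comparison on the primary endpoint that rests wholly on randomisation has about 40, with 10 in one arm.

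This is a written rule, not a detail left open: a programmer who follows the SAP must use z. At stake is whether a p-value just below 0.05 would still be below it under a suitable reference. This matters most in the 30 v 10 analysis, which serves as the check on the estimate that uses historical controls.

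**Working it through.** **Inputs.** The test is two-sided at 5% (SAP 11.1). Planned numbers are 30 dornase alfa, 10 randomised control and 60 matched historical controls, 100 in all (SAP 12). The subject-level terms are intercept, treatment, age, gender, BMI, baseline CRP and key comorbidity, which makes seven parameters (SAP 8.2 and 11.1). Time and treatment-by-time vary within patient and are not counted.

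**1. The plan's own sample size.** SAP 5 states: "Based on a mean of 99mg/L in the control group and a common standard deviation of 62mg/L derived from the literature", and that "a total sample size of 90 participants would provide sufficient power to detect a greater than a 40% relative difference for CRP". The difference is 0.40 × 99 = 39.6 mg/L. With 30 active and 60 control patients:

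- standard error = 62 × √(1/30 + 1/60) = 13.86
- noncentrality = 39.6 / 13.86 = 2.86
- power of the two-sample t test (88 df) = 80.7%

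The smallest total at 1:2 that reaches 80% is 90, so the stated figure is reproduced. The normal approximation gives 58 controls and a total of 87. The planned number is thus consistent with a t test, although the documents do not say which test was used.

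**2. Size of the z test.** Assume that the statistic follows a t distribution with df = N − 7. This is a proxy for the mixed model. For the AUC regression it is the residual df. Then

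true size = 2 × P(T_df > 1.96).

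| Analysis | N | df | t critical value | True size | t/z ratio |
|---|---|---|---|---|---|
| Primary, or AUC on the same set | 100 | 93 | 1.986 | 5.30% | 1.013 |
| Dornase alfa v historical controls | 90 | 83 | 1.989 | 5.34% | 1.015 |
| Randomised control v historical controls | 70 | 63 | 1.998 | 5.44% | 1.020 |
| Randomised only, 30 v 10 | 40 | 33 | 2.035 | 5.85% | 1.038 |
| Randomised only, 36 v 12 (maximum) | 48 | 41 | 2.020 | 5.68% | 1.030 |

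**3. Where a decision would change.** The z-based p-value at the t critical value is 2 × P(Z > 1.986) = 0.047 in the primary analysis and 2 × P(Z > 2.035) = 0.042 in the 30 v 10 analysis. Only results between these values and 0.050 change sides. For example, a z-based p of 0.040 becomes 0.043 in the primary analysis and 0.048 in the 30 v 10 analysis, and stays below 0.05 in both.

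**4. Simulation check on the mixed model.** Each setting used 10,000 null trials with a random intercept, four visits and an intraclass correlation of 0.3 or 0.6. All of these are assumptions. The Monte Carlo standard error is 0.2 to 0.3 percentage points. Rejection rates with the z reference were:

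| Comparison | REML | ML |
|---|---|---|
| 30 v 70 | 5.1% | 6.1% |
| 30 v 10 | 6.1–6.3% | 8.7–8.8% |

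The REML results agree with step 2 in direction and rough size. The ML column applies only if ML is used, which the SAP neither states nor rules out.

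**The case against.** The strongest reply is that the effect on the primary analysis is too small to matter. The REML simulation gives 5.1%, which cannot be told apart from 5% given its Monte Carlo error, and a large-sample Wald reference with about 100 patients is common. In a small open-label Phase IIa trial with non-randomised historical controls in the main comparison, other sources of error will be larger. This stands, and it makes the point a minor one.

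The 30 v 10 analysis is also an additional one. SAP 8.3.1 says that its estimate will be set beside the primary estimate. It states no significance threshold there, so the z rule reaches it only by inference from 11.1. This stands too, and the 5.85% is conditional on it.

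A reader might infer more than the documents support:

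- **That the interim test is inflated.** The interim result places conditional power in a zone (SAP 12), and Protocol 11.4 says that there is no formal comparison between groups. No 5% test is planned there.
- **That the SAP overrides a t test supplied by the software.** SAS is named for randomisation and sample size only. No software is named for these models.
- **That the t test would be exact for the AUC regression.** This needs normal errors of equal variance. Each area is divided by the patient's own follow-up time, so equal variance is doubtful. The t reference is better than z, but still approximate.
- **That the planned confidence intervals are too narrow.** SAP 11.1 prescribes the normal only for the p-value.
- **That 30 v 10 is the only fully randomised comparison in the trial.** It is the only one for the primary endpoint. The WHO ordinal score is also analysed in randomised patients alone.

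What survives is the written rule itself. The z reference has no advantage here, and the correction is almost free.

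**Conclusion.** The point holds as a small, easily corrected fault. Both p-value rules in SAP 11.1 are slightly anti-conservative. The excess over 5% is about 0.3 percentage points in the primary analysis by the t calculation and about 0.1 in the REML simulation. In the 30 v 10 analysis, if the rule carries over, it is about 0.85 points by the t calculation and 1.1 to 1.3 in the REML simulation. If the confidence intervals also used z, t-based intervals would be 1.3% and 3.8% wider respectively.

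A reader might conclude that the trial's 5% error rate is materially broken. The documents do not support that, because a primary conclusion would change only within a very narrow band of p-values. The figures rest on N − 7 as a stand-in for the mixed-model degrees of freedom and on the assumed visit pattern, random intercept and intraclass correlation. Analyses stratified by best-available-care treatment (SAP 8.3.1) may have fewer patients and a larger error, but their sizes are not given.

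**What to change.** In SAP 11.1, replace the standard normal reference as follows:

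- For the mixed-model contrast and its confidence interval, state REML, Kenward-Roger (or Satterthwaite) degrees of freedom and the t distribution.
- For the AUC regression, state the t test on the residual degrees of freedom (93 at 100 patients).
- Say that the same rule applies to the additional and stratified analyses in 8.3.1, and to the secondary endpoints in 11.2 that reuse the primary model.

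This also settles the choice between REML and ML, and it keeps p-values and intervals consistent with each other. It costs a sentence or two in the SAP and a software setting. No extra data or patients are needed. The only downside is slightly larger p-values. If results have already been produced, report the change as a deviation under Protocol 11.5 and show both p-values.

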# 6.1 Primary analysis population (Intention to treat)

The primary analysis population will be all evaluable patients randomised to BAC + dornase alfa or BAC only who have at least one post-baseline CRP measurement, as well as matched historical comparators.

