### 6.2 Per protocol population

The per protocol (PP) population will be all evaluable patients randomised to BAC + dornase alfa or BAC only, as well as matched historical comparators, excluding important protocol violations. Important protocol violations will be defined as:

- Initiated dornase-alfa prior to Dexmathasone.
- Withdrew from the study prior to 7 days follow-up.
- Discontinued the study drug prior to discharge from hospital or 7 days follow-up.

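### The supplementary CRP analysis matches on and adjusts for a last pre-dexamethasone CRP that need not precede randomisation, so for some dornase alfa patients it can be an on-treatment value

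*SAP*

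**What the plan says.** In the primary model (SAP 11.1) the CRP covariate is "defined as the last CRP measurement prior to randomisation, or the first CRP following Dexamethasone for HCs". For randomised patients it is therefore a pre-treatment value.

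The SAP adds a supplementary analysis with a different CRP variable, used in two places:

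- **Matching (SAP 11):** "the matching will be done using the last pre-Dexamethasone CRP measurement, as well as the other factors defined above".
- **Model (SAP 11.1):** "as a supplementary analysis, the primary analysis will be performed, but including the HCs from the second propensity score matching analysis", and "the model will be adjusted for their last pre-Dexamethasone CRP as opposed to baseline CRP".

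The variable is tied to the start of dexamethasone. Neither section says that it must come before randomisation or the first dose of dornase alfa. SAP 10.2 lists it among the baseline characteristics, again without that condition.

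SAP 6.2 shows that the reverse order of the two drugs was foreseen. One of the important protocol violations is "Initiated dornase-alfa prior to Dexmathasone". That exclusion applies only to the per protocol population. The primary analysis population in SAP 6.1 is "all evaluable patients randomised to BAC + dornase alfa or BAC only who have at least one post-baseline CRP measurement", plus the matched historical controls, with no condition on the order of the drugs.

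**The concern.** A covariate in a treatment comparison should not be open to influence by the treatment. In a patient who starts dornase alfa first and dexamethasone some days later, the last CRP before dexamethasone may have been taken while on dornase alfa. It then takes the place of baseline CRP. It may also be one of the same patient's outcome values, because SAP 11.1 keeps CRP up to 7 days after randomisation and does not remove the value used as covariate.

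If dornase alfa lowers CRP, adjusting for a value that is already lower removes part of the effect. The matching works in the same direction, because it favours historical controls with correspondingly lower CRP.

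This is also the only planned analysis that takes the CRP variable before dexamethasone in the historical controls. The primary baseline for them is the first CRP after dexamethasone. The supplementary result will therefore naturally be set beside the primary one, and a known tendency towards no effect would make that comparison hard to read.

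A second gap is that a randomised patient who never receives dexamethasone has no value for this variable, and the plan gives no rule for that case.

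**Working it through.** **1. The plan's own figure.** The only figure to reproduce is the total of 90 in SAP 5. With a control mean of 99 mg/L, SD 62 mg/L, difference 0.40 × 99 = 39.6 mg/L, two-sided 5% and a 1:2 ratio, a two-sample t-test has power 0.807 at 90 and 0.793 at 87. The figure of 90 is reproduced. The point below does not depend on it.

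**2. Which CRP value is used.** Take an illustrative patient who starts dornase alfa on Day 1 and dexamethasone on Day 4, with CRP drawn on Days 1, 3, 5 and 7 as in SAP 3.

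- Primary model: the covariate is the last CRP before randomisation. Day 3 is an outcome.
- Area-under-the-curve analysis: same covariate, on the log scale.
- Supplementary analysis: the covariate is the Day 3 value, after two days of treatment. Day 3 is also an outcome.

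Only a patient with a CRP between first dose and a later dexamethasone start is affected.

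**3. Size of the bias.** Let τ be the true effect, b the slope of outcome on covariate, p the share of active patients affected, and f the fraction of τ already present in their covariate. The covariate mean in the active arm shifts by p × f × τ. The adjusted difference is then

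τ − b × (p × f × τ) = τ × (1 − b × p × f),

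so the proportion lost is about b × p × f.

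The documents give none of b, p or f. Assumed ranges are b from 0.3 to 0.7, p from 5% to 30%, and f from 0.25 to 1. The last column takes a true 40% reduction, τ = ln 0.6 = −0.511, and computes 1 − exp[τ(1 − bpf)].

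| b | p | f | Effect lost | A 40% reduction reads as |
|---|---|---|---|---|
| 0.3 | 5% | 0.25 | 0.4% | 39.9% |
| 0.5 | 10% | 0.5 | 2.5% | 39.2% |
| 0.5 | 20% | 0.5 | 5% | 38.4% |
| 0.5 | 30% | 1 | 15% | 35.2% |
| 0.7 | 30% | 1 | 21% | 33.2% |

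In patient numbers, one of 30 at b = 0.5 and f = 0.5 gives 0.5 × 1/30 × 0.5 = 0.8%. Three of 30 at b = 0.8 and f = 0.5 gives 0.8 × 3/30 × 0.5 = 4%.

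**4. Check by simulation.** A covariance analysis on the log scale (30 active, 70 control, b = 0.5, log SD 0.7, 4,000 runs) gave losses of 2.3%, 5.2% and 14.6% for the three middle rows. With a covariate taken before treatment the estimate was −0.511, so nothing was lost.

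**5. In terms of power.** With 60 against 30 patients, the planning inputs and a normal approximation, power is 0.815 with no loss. It is 0.795, 0.774 and 0.680 at losses of 2.5%, 5% and 15%. This is only an indication, because the planned model is a repeated-measures model.

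The simulation has one outcome per patient and no matching step. The effect of matching is a direction by reasoning and has not been quantified.

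**The case against.** The case on the other side has real substance.

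- **Scope.** One supplementary analysis is affected. A reader might infer that the primary p-value or the area-under-the-curve result is biased in this way. The documents do not support that, since both use a pre-randomisation CRP for randomised patients. This stands.
- **Intent.** SAP 6.2 treats dornase alfa before dexamethasone as a violation, and SAP 10.2 lists the variable as a baseline characteristic. Both suggest that a pre-treatment value was meant. That is probably so, but the rule as written does not secure it.
- **Existing safeguards.** Protocol 11.3.4 repeats the primary and secondary analyses in the per protocol population, which would exclude these patients. SAP 11.1 specifies no such run for this analysis. That population also drops withdrawals and discontinuations, so a change in the result could not be traced to this problem. SAP 10.1 and 10.2 do report the number of violations and the days between dexamethasone and baseline, so the affected patients would be partly visible.
- **Size.** Pushing the inputs to b = 0.8, p = 50% and f = 1 gives 0.8 × 0.5 × 1 = 40%. This needs 15 of 30 active patients to commit an important violation with the whole effect already present. Nothing in the documents supports such inputs.
- **Direction.** Patients who start dexamethasone late may be those whose CRP is rising for other reasons, which could offset the shift. The bias towards no effect is conditional on the drug lowering CRP and a positive slope.
- **Further inferences.** A reader might infer that patients never given dexamethasone drop out of this analysis, or that a weaker result would be read as confounding in the primary one. Neither is stated. SAP 9.1 says that all available data enter all models, but a mixed model does not by itself supply a missing covariate. The accurate statement is that the rule is undefined. SAP 11 and 11.1 give no purpose or reading rule for this analysis.

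**Conclusion.** The gap is real and minor. As written, the supplementary analysis can match on and adjust for a CRP taken on dornase alfa, in patients whom the SAP itself foresees and keeps in the population used. If the drug lowers CRP, this biases that analysis towards no effect.

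The loss is about b × p × f. It is under 1% if very few patients are affected, and about 20% only if 30% of active patients are affected with the full effect already present. All three inputs are assumptions. The missing rule for randomised patients never given dexamethasone is a separate gap in the same definition. Because the bias is foreseeable and removable, this is more than a matter of wording, but it does not touch the trial's main conclusion.

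**What to change.** In SAP 11, SAP 11.1 and the baseline list in SAP 10.2, define the variable as follows:

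- **Randomised patients, both arms:** the last CRP before the earlier of dexamethasone start and randomisation. If dexamethasone is never given, the last CRP before randomisation.
- **Historical controls:** the last CRP before dexamethasone, as now.

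Report, by arm, how many randomised patients started dexamethasone before randomisation, started it afterwards, or never received it.

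For randomised patients the covariate then always precedes treatment, so p = 0 and the loss is zero. The cost is one sentence of definition, carried into those three places, and one change to a derived variable. No new data, sample size or clinical rule is involved.
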